Patients with a diagnosis of cerebrovascular event (CVE) will be recruited upon arrival at the PMRUcXXI in the first-time appointment area. The diagnosis will be verified and an appointment will be made to the office of one of the researchers (evaluator 1). During the appointment the purpose of the study will be explained and doubts will be clarified. Whether they accept or not, the patient will receive the consultation that is normally provided to this type of patient and the information will be recorded in the clinical record. If patient do not accept, after the consultation, the appropriate management for your condition will be prescribed and a subsequent appointment will be made with the corresponding doctor to continue the control. In case of agreeing to participate, a summary will be made in Annex 4, which includes demographic data, whether or not is a worker, the need for temporary disability for work and clinical data for the research file. The signature of the informed consent letter will be also requested (Annex 3). This physician 1 will assign the therapeutic modality by using a table of random numbers to: Group 1. Therapy supported by virtual reality; Group 2. Therapy supported by constraint-induced movement; o Group 3. Usual physical and occupational therapy. An appointment will then be made to be assessed by the second doctor (evaluator 2), who will remain blind to the treatment, and will measure the functionality of the thoracic and pelvic limbs with the different scales, described in the procedures section, including muscle tone, trophism, ranges of mobility, functionality of the limbs, as well as of the hand, coordination, balance, sensory aspects and language (Annex 2). The limb functionality scales will be applied before (initial assessment -V.I.), during (intermediate assessment -V.Int.- week 3, session 6) and after (final assessment -V.F.- week 6, session 12) of the performance of the different rehabilitation programs. At the same times, the Boston Aphasia Intensity Scale and the Intrinsic Motivational Inventory will be applied by a neuropsychologist blinded to the treatment.

Procedures.

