2. Extremity motor assessment. The patient will be admitted to consulting room 22, by appointment, where he will be received by physician 2 (blinded evaluator), who will have the indication to address the patient specifically in relation to obtaining data during the physical examination (actions to obtain the evaluation with scales). He will introduce himself and establish a rapport with the subject, but remind him that this assessment is related to an investigation and insist that he not give more information than what he requests. The evaluating physician will not know the therapeutic modality that the patient will receive. Afterwards, he will ask you to sit on the examination table and the clinical review related to the functionality of the hemibody will begin. The evaluation will begin with the motor index scale, then the quality of the fine forceps will be measured, and finally the Fugl Meyer scale. The assessment will be made before starting therapy, half the number of sessions (3 weeks) and at the end of treatment (6 weeks).

- a) **Evaluation with Fugl Meyer scale.** This scale is specific to the Cerebral Vascular Event, designed with the objective of measuring the motor deficit, balance, sensitivity and state/pain of the joints of patients who present hemiplegia/hemiparesis as a consequence of the event. In clinical practice it helps to assess the severity of the deficit, describe motor recovery, plan rehabilitation treatment and monitor the clinical evolution of patients after a stroke.

The result of this scale is measured in a numerical score, the higher numerical score corresponds to a better state of the patient's functioning. The scale is built to give ratings separately (both members, balance and sensitivity), but it can also be used globally, with a maximum of 226 points. The questionnaire must be administered by the evaluating physician, it contains 113 items encompassed in 5 domains that in turn cover three dimensions of the state of functioning and functionality in the EVC. For each item, the examiner must grant the corresponding qualifications indicated in each section.

Fugl-Meyer scale (spanish versión).

Dimension: Assessment of motor function in the upper limb.

Dominio	Item	Ini. Val.	Interm. Val	Fin. Val.
I. Osteotendinous reflexes 0: no reflexes 2: reflexes are obtained	1. Biceps 2. Triceps			

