Minimal observable impairments in speech. The patient may present subjective difficulties that are not evident to the listener.	5

e) **Evaluation of satisfaction when performing rehabilitation therapy.** The characterization of the patient's perception of satisfaction will be evaluated by the same neuropsychologist, who will be blinded to the treatment the patient is receiving, using the Intrinsic Motivation Inventory (IMI). The IMI is a multidimensional measurement device intended to assess the subjective experience of participants related to an objective activity in experiments; it has been used in various experiments related to intrinsic motivation and self-regulation. The instrument assesses participants' interest/enjoyment, perceived competence, effort, value/utility, felt pressure and strain, and perceived choice while performing a given activity, yielding six subscale scores. The concepts of perceived choice and perceived competence are theorized to be positive predictors of both self-report and behavioral measures of intrinsic motivation, and pressure/strain is theorized to be a negative predictor of intrinsic motivation. Effort is a separate variable that is relevant to some motivation questions, so it is used as relevant. The value/utility subscale is used in internalization studies, with the idea that people internalize and self-regulate with regard to activities that they experience as useful or valuable to themselves.

The subscales and items are:

Intrinsic Motivation Inventory (Assessment of satisfaction when performing rehabilitation therapy)
 (Spanish versión)

	Reality Virtual			Restriction and Induction of Movement			TF and TO habitual		
Patient perception	Ini. Val.	Interm. Val.	Fin. Val.	Ini. Val.	Interm. Val.	Fin. Val.	Ini. Val.	Interm. Val.	Fin. Val.
Interest and satisfaction with treatment									
As he worked on the task he thought how much he enjoyed it.									
I found the task very interesting.									
Doing homework was fun.									
I really enjoyed doing homework.									
I thought the homework was very boring (R).									
I seemed the task very interesting.									
I would describe the task as very pleasant.									
Perception of competence (of the patient versus the treatment)									
I think I'm very good at this task.									
I think I did very well in this activity, compared with other									
I am satisfied with my performance in this task.									
I felt quite skilled at this task.									

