After working on this task for a while, I felt quite competent.									
Effort and importance of treatment									
I felt it was my choice to do the task.									
I didn't really have the option to do task (R).									
I felt like I was doing what I wanted to do while working on the assignment.									
I felt that I had obligation to do task (R)									
I did the homework because I had no other option (R).									
Stress or strain (caused by treatment)									
I didn't feel nervous about doing task (R).									
I felt tense while doing task.									
I felt relaxed while doing task (R).									
I was anxious while doing task.									
I felt stressed while doing task.									

Ini. Val.: initial valoration; Intermed. Val.: intermediate valoration; Fin. Val.: final valoration.

Subscale scores can be used as dependent variables, predictors, or mediators, depending on the research questions being addressed. The higher the score, the higher the satisfaction.

3. Therapy programs.

- a. Virtual reality program. The activities indicated in the tennis and ski software for the upper limb, covering cracks for both limbs and Star Wars-battles in the galaxy for the hand and fine pincer,

which will be carried out with the interface of the virtual reality equipment "connected" to the patient through movement sensors, with the multiperceptual feedback of the Kinect equipment or with googles.

b. *Movement restriction and induction therapy.* The patient will be placed a sling on the "healthy" thoracic limb, attached to the thorax, through a bra, gently but firmly, in such a way that it does not alter circulation or compress peripheral nerves. It will be explained to you that you should do all your activities with the "sick" member, to the extent possible. The restriction of the healthy side forces the patient to put all his effort into carrying out the activities of daily life, simulated during the therapy. This restriction will be carried out for 1 hour in therapy in the medical unit. And the patient will be told to repeat it at home at least once a day for one to five hours, without receiving support from family members while wearing the sling.

c. *Regular physical and occupational therapy.* The specific activities are shown in Annex 1. They include:

- **Motor management:** tasks to promote mobility of the shoulder, elbow, pentadigital clamp, fine clamp, transfers; volitional movements, eye-motor coordination, hip, knee, ankle and gait mobility.

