- **Sensory training:** deep sensitivity, stereognosis, sensory discrimination, graphesthesia, topognosis and proprioception.

4. *Concentration and analysis of information.* The results of the different evaluations will be noted on the information capture sheet (Annex 2 and 4); Subsequently, they will be entered into an Excel spreadsheet and finally exported for analysis to the SPSS V-19 program.

STATISTICAL ASPECTS

Sampling

Non-probabilistic, of consecutive cases.

Sample size

The sample size calculation was performed to test the working hypothesis* (average difference of 38.6 points and a SD 12.23), with a standardized effect size greater than 1 in a prefabricated table to establish mean differences (Appendix 1. 13 -A)⁵², considering a unilateral hypothesis, in a finite population and without replacement, with a value $\alpha = 0.05$ and $\beta = 0.10$.

For 17 patients plus 20% of possible losses, for a total of 19 patients per group.

* The score of the motor evolution evaluated with the Fugl-Meyer scale was considered, with therapy supported by virtual reality, found in the study of the unit, considered as a pilot^{47, 48}.

Statistic analysis

Descriptive statistics will be carried out for the qualitative variables through tables, graphs and percentages; for the quantitative ones, measures of central tendency and its corresponding dispersion will be used, depending on the distribution of the data. The distribution of the numerical data will be compared with the distribution curve using the Shapiro-Wilk test, depending on the result, the ANOVA or Friedman test will be used for intragroup comparison; for comparison between groups, ANOVA of repeated measures or the Kruskal-Wallis test will be used. In case of detecting variables that could be potentially related to the result, correlation tests such as Pearson or Spearman will be applied. An α value of 0.05 will be considered.

ETHICAL ASPECTS

This research respects the institutional, national and international standards that govern research on human beings in our country. Including the General Health Law, TITLE FIVE Research for Health, sole chapter ⁵³; the regulation of the General Law of Health in Matters of Research for Health ⁵⁴; and the Official Mexican Standard NOM-012-SSA3-2012, which establishes the criteria for the execution of research projects for health in human beings ⁵⁵.

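### The Intrinsic Motivation Inventory is scheduled before therapy starts, when about 20 of its 22 items have nothing to refer to, and the plan does not keep that score out of the tests over time

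*Combined protocol and SAP*

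**What the plan says.** All references are to the combined protocol and SAP.

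- **Timing (Study General description).** For the limb scales: "The limb functionality scales will be applied before (initial assessment -V.I.), during (intermediate assessment -V.Int.- week 3, session 6", with the third assessment at session 12 in week 6. For the inventory: "At the same times, the Boston Aphasia Intensity Scale and the Intrinsic Motivational Inventory will be applied by a neuropsychologist blinded to the treatment".
- **First motor assessment (Procedures, 2. Extremity motor assessment).** "The assessment will be made before starting therapy, half the number of sessions (3 weeks) and at the end of treatment (6 weeks".
- **What the inventory captures (Procedures, 2 e).** It covers interest, competence, effort, value, pressure and "perceived choice while performing a given activity, yielding six subscale scores". Its items include "As he worked on the task he thought how much he enjoyed it", "After working on this task for a while, I felt quite competent" and "I felt tense while doing task".
- **Form (Procedures, 2 e, and Annex 2).** Each arm has an initial, an intermediate and a final column.
- **Purpose (Secondary questions).** The plan asks how satisfied patients are with the therapy they had, and how that satisfaction relates to adherence.
- **Use of the score (Variables, patient satisfaction, Indicators).** The summed score is said to be comparable between groups and within one person across occasions.
- **Analysis (Statistic analysis).** Depending on normality, "the ANOVA or Friedman test will be used for intragroup comparison", with repeated-measures ANOVA or Kruskal-Wallis between groups. The inventory is not named and its initial value is not excluded.

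**The concern.** A questionnaire about the experience of doing a task needs a task that has been done. At the initial assessment there has been no session, and the plan neither says what the task is at that visit nor provides a version worded as expectation. Random assignment comes before this assessment, so a patient who answers anyway may be reporting what they expect of the assigned therapy.

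If that value becomes the first of three occasions in a within-arm test, a significant result need not mean that satisfaction changed during therapy. It may show only that answers given before therapy sit at a different level from answers given after it. A reader could then report that one therapy raised satisfaction when the data show no such thing.

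**Working it through.** **1. Is one administration before therapy?** Study General description ties the inventory to the times of the limb scales, and the first of those is before the programmes. Procedures 2 confirms that the first motor assessment precedes therapy. The initial column on both copies of the form agrees with this.

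**2. How many items presuppose a task already done?** My count from the item list in Procedures 2 e):

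| Subscale | Items | Past tense about the task |
|---|---|---|
| Interest and satisfaction | 7 | 6 |
| Competence | 5 | 3 |
| Effort and importance | 5 | 5 |
| Stress or strain | 5 | 5 |
| Total | 22 | 19 |

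The competence item on satisfaction with one's own performance is in the present tense but also needs a performance: 19 + 1 = 20. The other 22 − 20 = 2 items (whether the task is pleasant, and whether one is good at it) could be answered in anticipation.

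**3. Could the initial value affect a test?** The plan gives no figure to reproduce, so this is an illustration under stated assumptions. The sample size section supplies n = 17 per arm before losses, and Statistic analysis supplies α = 0.05. The rest is assumed:

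- Scores at sessions 6 and 12 for patient i are sᵢ + e₁ᵢ and sᵢ + e₂ᵢ, where s and e are normal with mean 0 and SD 0.7. The total SD is √(0.49 + 0.49) = 0.99. Satisfaction is truly equal at the two sessions.
- The initial score is normal with mean −δ and SD 1, unrelated to the later scores.
- There are 3,000 simulated arms for each δ.

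| δ (SD) | Friedman, three occasions: p < 0.05 | Wilcoxon, session 6 v 12: p < 0.05 |
|---|---|---|
| 0 | 4.5% | 4.3% |
| 0.25 | 8.9% | 3.8% |
| 0.5 | 22.5% | 5.2% |
| 1 | 64.5% | 4.6% |

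The model is symmetric, so initial answers that are higher by the same amount would give the same rates and would look like a fall in satisfaction. With no shift, the Friedman test keeps its nominal level.

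**4. Does attendance vary enough for the adherence question?** Under Elimination criteria, patients who complete less than 90% of the programme are eliminated. 0.90 × 12 = 10.8, so a retained patient has attended 11 or 12 sessions.

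**The case against.** **The three-visit test of the inventory is inferred.** Statistic analysis never names it. The variable is labelled qualitative and ordinal, and that section gives qualitative variables only tables, graphs and percentages. This stands as a limit on certainty. It is not decisive, because the Fugl-Meyer scale carries the same label although the working hypothesis compares it in mean points.

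**The timing has a loose end.** Procedures 1 mentions the neuropsychologist's appointment after the patient is taken to the therapists, and gives it no date. The first inventory could on that reading follow some therapy. Study General description is the explicit statement and the initial column agrees with it, so the doubt does not displace the reading used here. If a later first administration was intended, the text still needs correcting.

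**Stronger readings that the documents do not support.**

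- A reader might infer that the initial score is meaningless. Two items can be answered in advance, and an expectation score can be interpreted if it is labelled as one.
- A reader might infer that a change-from-baseline comparison between arms is contaminated, or that two of three pairwise visit contrasts are lost. The plan specifies neither analysis for the inventory.
- A reader might take the printed columns as proof that every initial form is completed. The form has nine columns, three for each arm, and a patient belongs to one arm. It is a template.
- A reader might assume that every initial answer reflects a known arm. Allocation comes first, but the plan does not say when the patient is told.

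**Conclusion.** The point holds as a minor one. The plan schedules the inventory before therapy, about 20 of its 22 items then have no referent, and nothing keeps that score out of the repeated-measures or Friedman tests. How far this would distort a within-arm result depends on the unknown gap between initial and later answers. In the illustration, false significance runs from about 5% with no gap to about 65% with a gap of 1 SD. Those rates rest on the assumed distribution, on initial answers unrelated to later ones, and on the inference that the generic tests apply to the inventory.

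The effect is confined to a secondary outcome. Comparisons between arms at session 6 and at session 12 remain usable, and the motor and language scales have a proper baseline.

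**What to change.** 1. In Study General description, give the inventory at sessions 6 and 12 only. If initial forms have already been collected, label them as expectation, report them descriptively, and exclude them from the repeated-measures ANOVA and the Friedman test.
2. In Statistic analysis, name the inventory. Compare arms on the session-12 score, with session 6 as supportive. Limit any within-arm comparison to those two occasions.
3. For the adherence question, use the session-12 score. State that attendance has almost no range (11 or 12 sessions) if patients below 90% completion are eliminated, so a correlation in retained patients alone would say little.
4. Align the forms in Procedures 2 e) and Annex 2 with these changes, and date the neuropsychologist's appointment in Procedures 1.

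The cost is the loss of a pre-therapy score and a small change to an approved procedure. The activity schedule marks recruitment as carried out, so relabelling and excluding the value may be the version that applies. That version needs no new data, visits or patients.

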II. Flexor synergy 0: does not perform the action 1: does it partially 2: it does it perfectly	3. Scapular elevation 4. Shoulder retraction 5. Shoulder abduction 6. External rotation of the shoulder 7. Elbow flexion 8. Supination of the forearm			
III. Extensor synergy 0: does not perform the action 1: does it partially 2: it does it perfectly	9. Adduction/internal rotation of the shoulder 10. Elbow extension 11. Forearm pronation			
IV. Movements combining synergies 0: cannot perform the action 1: carry out the action partially (the hand must pass through anterior superior iliac) 2: it does it perfectly	12. Hand towards lumbar spine			
0: arm is abducted immediately, or elbow is flexed at start of movement 1: abduction or flexion of the elbow occurs at a later stage of the movement 2: perform the action perfectly	13. Shoulder flexed at 90°, elbow at 0°			
0: correct shoulder position and neither elbow flexion nor pronation/supination can be achieved. 1: active pronation or supination can be performed partially (shoulder and elbow are correctly positioned). 2: perform the action perfectly	14. Forearm pronation/supination, elbow at 90°, shoulder at 0°			
V. Movements that do not combine synergies 0: initial flexion occurs at the elbow, or some tendency to pronate the forearm. 1: the movement can be carried out partially, or, if during the movement, the elbow is flexed, or the forearm cannot be maintained in pronation. 2: it performs perfectly	15. Shoulder abduction up to 90°, elbow at 0°, forearm pronated			
0: elbow flexion is initiated, or the shoulder is abducted 1: elbow flexion or shoulder abduction occurs during shoulder flexion (later in the movement).	16. Shoulder flexion between 90-180°, elbow at 0° and forearm in intermediate position			

2: it performs perfectly				
0: supination and pronation cannot be performed. 1: properly positioned elbow and shoulder are properly positioned but supination is in range limited 2: it performs perfectly	17. Pronation/supination of the forearm, elbow at 0° and shoulder at 30-90° of flexion			
VI. Reflexes 0: at least 2 of the 3 reflexes are markedly hyperactive 1: one reflex is markedly hyperactive or at least 2 reflexes are present 2: no more than one reflex is present and none is hyperactive	18. Exploring Reflexes			

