0: the activity is performed in more than 6 seconds slower than by hand does not affect 1: between 2 and 5.9 seconds slower than with the unaffected hand 2: less than 2 seconds apart	50. Speed			
Sum of points obtained				
Partial score		#	/34 points	

Dimension: Assessment of balance

Dominio	Item	Ini. Val.	Interm. Val	Fin. Val.
0: do not sit without support 1: sits without support for a short time 2: sit without support for 5 minutes and adjust self posture	51. Sitting without support with feet suspended			
0: does not maintain the posture to avoid falling 1: partially holds the pose 2: maintains posture properly	52. Parachute reaction on the unaffected side			
0: does not maintain the posture to avoid falling 1: partially holds the pose 2: maintains posture properly	53. Parachute reaction on the affected side			
0: does not stand up 1: does not want important help from other person(s) 2: can be maintained for at least one minute with minimal or token assistance from another person	54. Standing with support			
0: does not stand up 1: standing 1 minute without oscillations 2: good balance (+1 minute safely)	55. Standing without support			
0: holds the position for 1-2 sec 1: balance 4-9 sec 2: balance -10 sec	56. Mono-standing on the leg does not affect			
0: holds the position for 1-2 sec 1: balance 4-9 sec 2: balance -10 sec	57. Mono-standing on the affected leg			
Sum of points obtained				
Partial score		#	/14 points	

Dimension: Sensitivity

Dominio	Item	Ini. Val.	Interm. Val	Fin. Val.
Exteroceptive	58. Arm			
0) Anesthesia	59. Palm of the hand			
1) Hypoesthesia	60. Leg			
2) Normal	61. Sole of foot			
	62. Shoulder			
	63. Elbow			
Proprioceptive	64. Wrist			
0) No answer is correct	65. Fingers			
1) Diminished: $\frac{1}{4}$ of answers are correct	66. Hip			
2) All the answers are correct	67. Knee			
	68. Ankle			
	69. Toes			
	Sum of points obtained			
	Partial score	#	/24	points

Dimension: Joint range and joint pain

	Joint range 0: Just a few degrees of movement 1: Decreased passive mobility 2: Normal passive mobility				Joint pain 0: Pain in all ranges of motion and severe pain at the end of range of motion. 1: Mild pain 2: No pain			
Dimension	Dominio	Val. Ini.	Val. Int.	Val. Fin.	Dominio	Val. Ini.	Val. Int.	Val. Fin.
Shoulder	70. Abduction				71. Abduction			
	72. Flexion				73. Flexion			
	74. External rotation				75. External rotation			
	76. Internal rotation				77. Internal rotation			
Elbow	78. Flexion				79. Flexion			

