Dimension: Sensitivity

Dominio		Item		Ini. Val.	Interm. Val.	Fin. Val.
Exteroceptive 0) Anesthesia 1) Hypoesthesia 2) Normal		58. Arm 59. Palm of the hand 60. Leg 61. Sole of foot				
Proprioceptive 0) No answer is correct 1) Diminished: $\frac{3}{4}$ of answers are correct 2) All the answers are correct		62. Shoulder 63. Elbow 64. Wrist 65. Fingers 66. Hip 67. Knee 68. Ankle 69. Toes				
		Sum of points obtained				
		Partial score		#	/24 points	

Dimension: Joint range and joint pain

Dimension	Joint range				Joint pain			
	Dominio	Val. Ini.	Val. Int.	Val. Fin.	Dominio	Val. Ini.	Val. Int.	Val. Fin.
Shoulder	70. Abduction				71. Abduction			
	72. Flexion				73. Flexion			
	74. External rotation				75. External rotation			
	76. Internal rotation				77. Internal rotation			
Elbow	78. Flexion				79. Flexion			
	80. Extension				81. Extension			
Forearm	82. Pronation				83. Pronation			
	84. Supination				85. Supination			
Wrist	86. Flexion				87. Flexion			
	88. Extension				89. Extension			
Fingers	90. Flexion				91. Flexion			
	92. Extension				93. Extension			
Hip	94. Flexion				95. Flexion			
	96. Abduction				97. Abduction			
	98. External rotation				99. External rotation			
	100. Internal rotation				101. Internal rotation			
Knee	102. Flexion				103. Flexion			
	104. Extension				105. Extension			
Ankle	106. Dorsiflexion				107. Dorsiflexion			
	108. Plantar flexion				109. Plantar flexion			
Foot	110. Eversion				111. Eversion			
	112. Inversion				113. Inversion			
Sum of points								
Partial score					#	/ 44 points		
TOTAL score					#	/226		

Ini. Val.: initial valuation; Interm. Val.: intermediate valuation; Fin. Val.: final valuation.

Motor Index

Score	Action/ Movement	Reality Virtual			Restriction and Induction of Movement			TF and TO habitual		
		Ini. Val.	Interm. Val.	Fin. Val.	Ini. Val.	Interm. Val.	Fin. Val.	Ini. Val.	Interm. Val.	Fin. Val.
Sitting patient 0: no movement 9: palpable contraction 14: perform movement but not full range vs gravity 19: full range of motion vs gravity but not vs resistance 25: movement vs resistance but less than contralateral 33: normal strength	Shoulder abduction									
	Elbow flexion Voluntary movement of 90°									

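### The printed Fugl-Meyer scoring levels contradict each other or leave gaps; only reflex items 18 and 47 reach the motor scores, by one point each

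*Combined protocol and SAP*

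**What the plan says.** The Fugl-Meyer scale is printed twice: in Procedures, section 2a, and on the Annex 2 guide sheets. The points at issue are these.

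- **Items 1 and 2 (biceps, triceps), both copies:** "0: no reflexes 2: reflexes are obtained".
- **Item 18 (upper-limb reflexes), both copies:** level 0 is "0: at least 2 of the 3 reflexes are markedly hyperactive", level 1 is "1: one reflex is markedly hyperactive or at least 2 reflexes are present", and level 2 is "no more than one reflex is present and none is hyperactive". The three reflexes are not named.
- **Item 47 (lower-limb reflexes), both copies:** level 1 counts reflexes that are *present*, as in item 18, but level 2 counts reflexes that are *alive*. The item is rated only in patients who earned 4 points in the section before it.
- **Items 62 to 69 (proprioception):** level 1 is "Diminished: $\frac{1}{4}$ of answers are correct" in the procedures and "Diminished: $\frac{3}{4}$ of answers are correct" in Annex 2. In both copies level 0 means no correct answers and level 2 means all correct.
- **Items 56 and 57 (single-leg stance), both copies:** "0: holds the position for 1-2 sec 1: balance 4-9 sec 2: balance -10 sec".

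The scale table under Variables gives maxima of 66 for the upper limb, 34 for the lower limb and 226 overall. The text on score equivalence uses a 100-point motor score made up of the two limbs only. The work hypothesis concerns the upper limb.

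**The concern.** Fugl-Meyer is the scale of the work hypothesis and of the sample-size calculation, so its levels are operative measurement rules. Each item needs levels that cover every patient once. Where two levels apply, or none does, the rater must decide, and that decision could differ between the visits at baseline, session 6 and session 12.

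Item 18 has a further problem. Read literally, it withholds the top mark from a patient whose reflexes are simply normal. A patient who goes from one markedly hyperactive reflex to normal reflexes stays at level 1, so that recovery is not recorded.

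**Working it through.** **1. Stated maxima.** Each item scores at most 2.

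| Dimension | Items × 2 | Maximum |
|---|---|---|
| Upper limb | 33 × 2 | 66 |
| Lower limb | 17 × 2 | 34 |
| Balance | 7 × 2 | 14 |
| Sensitivity | (4 + 8) × 2 | 24 |
| Joint range | 22 × 2 | 44 |
| Joint pain | 22 × 2 | 44 |
| Total | 113 × 2 | 226 |

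All agree with the plan, and 66 + 34 = 100.

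**2. Item 18.** Assume that its three reflexes are biceps, triceps and one other. Each can be absent, present or markedly hyperactive, which gives 3³ = 27 states. Give the other 30 upper-limb items full marks (30 × 2 = 60).

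- Biceps and triceps both obtained: items 1 and 2 give 4. At least two reflexes are present, so item 18 is at most 1. Best total 60 + 4 + 1 = 65.
- Only one of them obtained: items 1 and 2 give 2. Item 18 can be 2. Best total 60 + 2 + 2 = 64.
- Neither obtained: best total 60 + 0 + 2 = 62.

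The maximum over all states is 65. In 7 of the 27 states (two or three hyperactive reflexes: 6 + 1) levels 0 and 1 both apply.

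The 65 depends on the assumption. If at most one of biceps and triceps is among the three, or if *present* was meant as *lively*, then 60 + 4 + 2 = 66 can be reached.

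**3. Item 47.** A patient with two or more elicitable reflexes, none of them lively or hyperactive, meets level 1 (at least two present) and level 2 (at most one lively). The difference is 1 point. The section before it has two items, so its 4-point condition means full marks there (2 × 2). The ambiguity therefore affects only patients with good recovery of those movements.

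**4. Proprioception, one item.**

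| Share correct | Procedures, literal | Annex 2, literal | Procedures, as minimum | Annex 2, as minimum |
|---|---|---|---|---|
| 0 | 0 | 0 | 0 | 0 |
| 1/4 | 1 | none | 1 | 0 |
| 1/2 | none | none | 1 | 0 |
| 3/4 | none | 1 | 1 | 1 |
| 1 | 2 | 2 | 2 | 2 |

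Read literally, half correct has no level in either copy. If the fractions are minimum thresholds (an assumption), a patient from 1/4 to just under 3/4 correct on every item differs by 8 × 1 = 8 points between copies.

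**5. Stance.** Read the top level as ten seconds or more. Holds under 1 second, between 2 and 4 seconds, and between 9 and 10 seconds then have no level. A 3-second hold can be placed at 0 or 1, so over two items the range is 2 × 1 = 2 points. Reading the dash as under ten seconds makes level 2 overlap levels 0 and 1 and leaves long holds unscored.

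**6. Where each defect counts.**

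| Items | Upper limb (66) | Motor (100) | Global (226) | Size |
|---|---|---|---|---|
| 18 | yes | yes | yes | 1 |
| 47 | no | yes | yes | 1 |
| 62–69 | no | no | yes, via sensitivity (24) | up to 8, threshold reading |
| 56–57 | no | no | yes, via balance (14) | up to 2 |

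**The case against.** The strongest reply is that these are transcription or translation slips with little effect on the result. Much of it stands.

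- The forms are labelled as the Spanish version, and the English is visibly translated. *Alive* in item 47 points to *lively* as the intended word in item 18. The wording the rater actually used cannot be seen.
- The 1/4 and 3/4 differ by one digit in a small fraction inside a broken table, and one may be a misreading of the PDF. Even so, half correct has no literal level under either. Item 18, the mixed wording of item 47 and the stance gap recur in both copies, which makes a reading error unlikely there.
- One blinded doctor rates every visit, and the schedule includes standardisation of procedures. A convention applied consistently would largely cancel in change scores and would not differ by arm. Nothing in the plan fixes that convention, however, so drift between visits is possible though not shown.

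A reader might infer that up to 8 points of scoring ambiguity bear on the hypothesis, and set them against the pilot's difference in Fugl-Meyer change (12.77 − 10.9 = 1.87 in Table 1). The documents do not support that. Proprioception is outside the upper-limb and motor scores, and Table 1 does not say which Fugl-Meyer score the pilot used.

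**Conclusion.** The point holds as a correction to the scoring sheet. The printed levels are inconsistent or not exhaustive in four places. Two of them, items 18 and 47, enter the motor scores at 1 point each, and only item 18 enters the upper-limb score. The 65-point maximum rests on a literal reading and on biceps and triceps being among item 18's three reflexes.

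Proprioception and stance affect only the sensitivity, balance and 226-point totals. The 8 points for proprioception need the threshold reading, and the 2 points for stance take the top level as ten seconds or more. The procedures mention the global 226-point total as a possible use.

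A reader might go further and conclude that the comparison between groups is biased. With one blinded rater for all arms, the documents give no ground for that. The likely effect is added noise and a small ceiling error.

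**What to change.** 1. In items 18 and 47, use the *lively* wording in both level 1 and level 2, as item 47 level 2 already implies, and name the three reflexes.
2. Reconcile the proprioception and stance levels in the procedures and Annex 2 with the validated Spanish form, so that every result falls in exactly one level. The cut-offs should come from that form, because the plan relies on the scales being validated in Spanish.
3. Use the same sheet at all three visits.
4. The study period runs from March 2020 to June 2024, so patients may already have been scored. State which sheet, and which reading of the ambiguous items, was used for them.

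The cost is a form correction and a short statement. No visit, assessment or patient is added.
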